10.3 Selection and Timing of Dose for Each Patient

Dosing will be initiated after the informed consent has been obtained and all necessary study eligibility assessments have been completed. Dosing will be according to the schedule of visits.

11.1 Blinding

This is a double blinded, placebo controlled study.

10. Prior and Concomitant Therapy

All prior and concomitant therapies will be assessed by the principal investigator if needed.

12.1 Prohibited Medications or Therapies During Study

Medications having the potential to interfere with the evaluation of efficacy are excluded throughout the trial and include:

- Antibiotic ear drops
- Steroid ear drops

12.2 Treatment Compliance

Treatment compliance will be assessed by the principal investigator following administration of FGF-2.

13.1 Schedule of Assessments

Visit	0	1	2	3	4	5	6	7	Final Visit
Screening	Day 1 (± 7 days)	Day 22 (± 7 days)	Day 43 (± 7 days) As Needed	Day 64 ⁵ (± 7 days) As Needed	Day 85 ⁶ (± 7 days) As Needed	Day 106 ⁶ (± 7 days) As Needed	Day 127 ⁶ (± 7 days) As Needed		F/U ⁷ (± 7 days) As Needed
Informed Consent	X								
Inclusion/Exclusion Criteria	X								
Medical History Related to the Tympanic Membrane	X								
Otologic Exam	X								X
Vital Signs	X ²	X ²	X	X	X	X	X	X	X
Laboratory Evaluation /CBC, Basic Metabolic Panel, HbA1C/	X								X
Pregnancy Test ³	X								
Prior/Concomitant Medication	X	X	X	X	X	X	X	X	X
TM photography	X ^{1,2}	X ^{1,2}	X ¹	X ¹	X ¹	X ¹	X ¹	X ¹	X
Audiology		X ^{1,2}	X ¹	X ¹	X ¹	X ¹	X ¹	X ¹	X
Tympanometry									X
Study Drug Administration	X	X ⁴	X ⁴	X ⁴	X ⁴	X ⁴	X ⁴		
Review of Adverse Events	X	X	X	X	X	X	X	X	X

¹To be completed prior to administration of the investigational drug.

²This may be performed during the screening visit or during Day 1 Visit. Note: The first audiogram may have been performed within 60 days prior to subjects' enrollment.

³Women of child bearing potential will be required to have a negative pregnancy test. Either serum or urine tests are acceptable. Until study completion, adequate form of contraception must be ensured.

⁴Treatment given if the perforation has not closed at this visit.

⁵If the perforation has not closed at this visit, then the subject will be assigned to the other treatment group. The subject will then follow the same schedule of procedures as stated for Visit 5, Visit 6, Visit 7, and Final Visit.

⁶These visits will be completed by subjects that have been assigned to the other treatment arm and whose perforation still has not closed.

⁷The final study visit occurs 2 months (+/- 7 days) after the subject's last follow-up visit. The subject's last follow-up visit occurs when the subject's perforation is determined to be closed, or when the subject has completed the maximum number of study visits without perforation closure

13.2 Efficacy Measurements

- Dose limiting toxicity/Optimal Biologic Dose is as defined in section 7.1
- TM closure is defined as complete closure of the tympanic membrane durable at both 21-days (± 7 days) and the test-of-cure Visit 5.
- TM Photographs will be obtained at every visit. A series containing pre- and post-treatment images will be digitally secured with Leica M320 high definition digital camera mounted with the Leica Microscope or with a 2.7 mm rigid Storz endoscope.
- Audiometric studies including pure tones (0.25, 0.5, 1, 2, 4, and 8 kHz) and speech discrimination scores will be recorded pretreatment and post treatment. A change of >10 dB across two frequencies or a change in speech discrimination of $> 20\%$ will be considered clinically significant on an NU-50 word list.
- Mobility of the tympanic membrane as measured by a Grayson Stadler GSI 37 Autotymp (Madison, WI) or equivalent tympanometer will be recorded when the TM appears healed otoscopically.

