4.1 Primary Objective

- To evaluate the efficacy of FGF-2 to repair chronic tympanic membrane perforations to complete closure as assessed by pre- and post-treatment photography when compared to placebo treated controls.

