- 2) After 15 minutes, the lidocaine infused cotton ball will be removed and the edge of the perforation roughened with a micropick to remove the epithelium circumferentially around the perforation edge.
- 3) A human fibroblast growth factor-2 (FGF-2) soaked pledget (approximately 20 µg in 0.2ml) of bioabsorbable gelatin sponge slightly larger than the tympanic membrane will then be placed against the lateral surface of the tympanic membrane to completely covered it. For the placebo group, only sterile water will be delivered by the pharmacy for saturation of the gelatin sponge.
- 4) The pledget will be secured in place with several drops of fibrin glue (Tisseel, McKesson Health Solutions, Auburndale, MA).
- 5) After the effects of the topical anesthetic have worn off, if any, the patient will be released with the following instructions:
 - a) Avoid violently sniffling or blowing the nose
 - b) Sneeze and cough naturally through the mouth without occluding the mouth with the hand.
 - c) Use cotton balls covered with petroleum jelly on the outer surface when washing the hair and bathing, to keep water out of the ear.
 - d) Avoid using a hearing aid in the treated ear.
 - e) Avoid flying, using elevators in tall buildings, and other situations involving substantial changes in air pressure.
 - f) Avoid swimming.
- 6) The subject will then come back at three weeks (+/- 7 days) for a follow- up appointment. The tympanic membrane will be examined to see if the perforation has closed and photographed in the same fashion as during the IMP or initial administration visit. Additional otologic tests will be performed during this follow up exam as well (See 13.1 Schedule of Assessments). If the tympanic

membrane has closed, then the participant will be seen again in approximately 2 months (+/- 7 days) for a final study visit.

However, if the perforation has not closed, then the FGF-2 or placebo application will be duplicated in the same fashion at this follow up visit. The subject will then be seen again at three weeks (+/- 7 days). The tympanic membrane will be assessed again. If the TMP is not healed, then a third application of the FGF-2 or placebo will be applied again at this visit. Additional otologic tests will be performed once again. If the TMP heals, then the subject will be seen again following this visit, or at approximately two months (+/- 7 days).

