Once the subject completes Visit 1, Visit 2, and Visit 3, the subject will come back for Visit 4 (+/- 7 days). During this visit, the perforation will be examined again. If the perforation has not closed completely at this visit, then the blind on the subject's randomization status will be broken. If the subject was randomized to placebo, s/he will be crossed over to receive unblinded FGG-2 treatment. If the subject was randomized to FGF-2 treatment, s/he will receive no further study treatment and return in two months (+/- 7 days) for the final follow up visit.

If crossed-over to unblinded FGF-2 treatment, the subject may be given up to three additional treatments. The follow up visits will occur three weeks (+/- 7 days) and the same otologic procedures will be conducted as mentioned before (See Section 13.1, Schedule of Assessments). If the perforation is found to be closed during these visits or when the subject has completed the maximum number of study visits without perforation closure, then the subject will report in 2 months (+/- 7 days) for a final visit. The study will be completed for reporting purposes after all subjects have completed the 2 month (+/- 7 days) follow up final visit.

6. Discussion of Study Design

The investigator and the subject will be blinded to treatment assignment during the Randomized Treatment phase. Subjects whose perforations fail to close during the randomized treatment phase will crossover to the Unblinded Crossover Phase. During the crossover phase, only those subjects who failed placebo will receive unblinded FGF-2 treatment. The rationale for using a dose of 20 μ g in 0.2ml is based on the maximum effective dosages as reported in humans of TMR closure with FGF-2 (Kanemaru et al., 2011).

The subjects, physician, and other study staff members will remain blinded to the treatment arm during the randomized treatment phase as the pharmacy will oversee the randomization process. During the Randomized Treatment phase, the pharmacy will provide the appropriately blinded vial of either FGF-2 or placebo solution as needed upon the request from the physician. Only those subjects who fail the randomized treatment phase will crossover into the unblinded crossover phase. Documentation of the cross-over will be made in the Case Report Forms as well as in the randomization log managed centrally by the dispensing pharmacy.

7. Selection of Study Population

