14.4 Visit 4, 64 days after the first treatment (± 7 Days)

The following procedures will be performed:

- Study Drug administration- *If the TMP is not completely closed, then the blind on the subject's randomization status will be broken. Placebo subjects will be crossed over to FGF-2 treatment arm at this visit.*
- Vital Signs
- Review of Prior/ Concomitant medication(s)
- TM photography
- Audiogram
- Assessment of Possible Adverse events

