14.5 Visit 5, 85 days after first treatment (± 7 Days)

This is a follow up visit for all subjects who were crossed over to the other treatment group at Visit 4. The following procedures will be performed:

- Study Drug administration- *if the TMP is not completely closed*
- Vital Signs
- Review of Prior/ Concomitant medication(s)
- TM photography
- Audiogram
- Assessment of Possible Adverse events

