14.8 Final Visit (2 Months Following Last Appointment, \pm 7 Days)

In order to complete the study, a final follow up visit will be completed. The following procedures will be performed:

- Otolgic Exam
- Vital Signs
- Laboratory evaluation (hematology and chemistry): *CBC, Basic Metabolic Panel Test, HbA1c*
- Review of Prior/ Concomitant medication(s)
- TM photography
- Audiogram
- Tympanometry
- Assessment of Possible Adverse events

15. Primary Safety and Efficacy Variable(s)

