17.5 Efficacy Analysis

Efficacy data from the Randomized Treatment phase will be evaluated by inspection, using student T-test, Cochran Mantel Hansel, or Kruskal-Wallis tests as appropriate; without conservation of alpha at 0.05. An interim analysis will be completed after approximately 50% of the study subjects (n=30) have been accrued.

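### Section 13.2 ties closure to Visit 5, a visit that no subject who closes in Part A is scheduled to attend

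*Combined protocol and SAP*

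**What the plan says.** Section 4, section 5.1 and the statistical paragraph of the synopsis make complete closure against placebo the primary outcome. Section 4.1 states the objective: "To evaluate the efficacy of FGF-2 to repair chronic tympanic membrane perforations to complete closure as assessed by pre- and post-treatment photography". Section 13.2 is the only place that adds a time rule. It requires "complete closure of the tympanic membrane durable at both 21-days (± 7 days) and the test-of-cure Visit 5".

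On who attends Visit 5, section 14.5 says: "This is a follow up visit for all subjects who were crossed over to the other treatment group at Visit 4". Footnote 6 to the Schedule of Assessments (section 13.1) likewise limits Visits 5 to 7 to subjects moved to the other arm whose perforation is still open.

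Closers follow another path. Section 5.1, step 6, says that if the tympanic "membrane has closed, then the participant will be seen again in approximately 2 months (+/- 7 days) for a final study visit". The synopsis study design and footnote 7 of the schedule agree. Section 14.8 says of that visit: "In order to complete the study, a final follow up visit will be completed". Its procedures include an otologic exam and TM photography.

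For subjects open at Visit 4, section 5.1 says: "If the subject was randomized to FGF-2 treatment, s/he will receive no further study treatment and return in two months". Section 14.4 says: "Placebo subjects will be crossed over to FGF-2 treatment arm at this visit". Footnote 5 of the schedule instead assigns any subject open at Visit 4 to the other treatment group.

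Section 17.5 gives the scope of the efficacy analysis: "Efficacy data from the Randomized Treatment phase will be evaluated by inspection".

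In the synopsis, the text under the primary endpoint heading is a schedule of examinations and safety checks. Closure stands under the secondary endpoints. Time to closure, a secondary objective in section 4.2 and a secondary outcome in section 5.1, is missing from that list.

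**The concern.** The closure definition depends on a visit that the subjects it should count as successes never reach. The analyst must therefore replace it, and at least two replacements are plausible: closed by Visit 4, or closed by Visit 4 and still closed at the Final Visit. They differ by every perforation that closes and then re-opens.

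The choice should be fixed before unblinded data are seen. Section 17.5 plans an interim analysis at about 30 subjects, and section 14.4 breaks the blind for each subject still open at Visit 4, so there is little time to leave it open.

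This is not a gap in data collection. Photography is scheduled at Visits 2, 3 and 4 and at the Final Visit. What is missing is a rule that can be applied.

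**Working it through.** The plan gives no figure for this point, so the check is a trace of visits followed by date arithmetic.

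**1. Who reaches Visit 5** (synopsis; sections 5.1, 13.1 and 14.3 to 14.8)

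| Status in Part A | Next scheduled visit | Visit 5? |
|---|---|---|
| Closed at Visit 2, either arm | Final Visit | No |
| Closed at Visit 3, either arm | Final Visit | No |
| Closed at Visit 4, either arm | Final Visit | No |
| Open at Visit 4, FGF-2 | Final Visit (section 5.1) or Visit 5 (footnote 5) | Documents disagree |
| Open at Visit 4, placebo | Visit 5, on unblinded FGF-2 | Yes |

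The conflict over FGF-2 subjects does not affect the result, because footnote 5 applies only to perforations that are not closed. Part A closers with a scheduled Visit 5 number 0 in each arm under either reading. At the synopsis sample size, the literal definition gives 0/45 against 0/15 (Fisher p = 1.0). That is a consequence of the rule and not an effect estimate.

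**2. Could Visit 5 mean the Final Visit?**

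Inputs: Visits 2, 3 and 4 at Days 22, 43 and 64; Visit 5 at Day 85 ± 7, so Day 78 to 92; Final Visit two months ± 7 days after the closure visit. Two months is taken as 61 days (assumption).

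| Closed at | Final Visit, nominal | ± 7 days | Meets Day 78 to 92? |
|---|---|---|---|
| Visit 2 | 22 + 61 = 83 | 76 to 90 | Yes |
| Visit 3 | 43 + 61 = 104 | 97 to 111 | No |
| Visit 4 | 64 + 61 = 125 | 118 to 132 | No |

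Taking 60 or 62 days changes none of these answers. Early visits can create an overlap for a Visit 3 closer: with Visit 3 on Day 36, the Final Visit can fall on Day 36 + 61 − 7 = 90. If each interval is 14 days, Visit 3 is on Day 29 and the Final Visit can fall on Day 29 + 61 − 7 = 83. A Visit 4 closer cannot overlap even then: Visit 4 is on Day 1 + 3 × 14 = 43, and 43 + 61 − 7 = 97, which is after Day 92.

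**3. Could Visit 5 mean Day 85 for everyone?**

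The time from closure visit to Day 85 would be 85 − 22 = 63, 85 − 43 = 42 or 85 − 64 = 21 days. The durability requirement would then depend on when the perforation closed. The Final Visit gives about 61 days for every closer.

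**4. How much the choice of rule could matter**

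The documents give no re-opening rate. As an illustration only, assume that 36 of 45 FGF-2 subjects (80%) are closed by Visit 4. Durable closures = 36 × (1 − re-opening rate), rounded:

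| Assumed re-opening | Durable closures | Rate |
|---|---|---|
| 0% | 36/45 | 80% |
| 5% | 34/45 | 76% |
| 10% | 32/45 | 71% |
| 20% | 29/45 | 64% |

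This shows one arm only and says nothing about the treatment difference.

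**The case against.** The contradiction itself is hard to dispute. The case on the other side concerns its weight and the remedy.

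- **The Final Visit is an inference.** No section calls it the test of cure. Closed by Visit 4 has support in sections 4 and 5.1, which speak of efficacy after up to three treatments. This stands in part: the sponsor could drop the durability condition. But section 13.2 asks for durable closure, and the Final Visit is the only scheduled visit that a Part A closer has after the closure visit.
- **Closure is described elsewhere.** Section 4.1 names photography, the synopsis names otoscopy and photography, and each visit applies a closed or not closed judgement. That is true, so what fails is the time and durability rule and not the notion of closure. None of those places supplies a time point.
- **The reference is an obvious slip.** Perhaps so, but section 13 has other broken references: 13.2 cites section 7.1 for dose-limiting toxicity, although 7.1 is the inclusion criteria, and 13.3 cites a section 7.7 that does not exist. The intended meaning cannot be assumed.
- **Part B closures are already kept out.** Section 17.5 confines efficacy to the Randomized Treatment phase, and salvage has its own objective. This largely stands. An explicit sentence in 13.2 would only complete that protection.
- **The synopsis point is minor.** This stands. The statistical paragraph of the same synopsis names complete closure as primary, so it is a heading error.

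**Conclusion.** The concern holds. As written, the closure definition in section 13.2 cannot be met by any Part A closer in either arm, whichever reading of footnote 5 is taken. This follows from the visit schedule alone and needs no assumption. That Visit 5 and the Final Visit do not coincide in general rests on taking two months as 60 to 62 days and on nominal dates, with the early-visit exception for Visit 3 closers shown above.

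The effect on the closure rate cannot be estimated from the documents; the 80% to 64% range is illustrative. The sentence in 13.2 must be corrected because it governs the primary outcome. The synopsis headings are a lesser matter, and the footnote 5 conflict is separate and does not bear on this result.

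**What to change.** In section 13.2, replace the Visit 5 reference with the Final Visit. Define success as complete closure at Visit 2, 3 or 4 that is still present at the Final Visit. In the same place, state that:

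- a subject not closed at Visit 4 is a Part A failure for this endpoint, whatever happens in Part B;
- a subject who closes and then re-opens before the Final Visit is not a success, however few applications were given;
- a closer who misses the Final Visit is classified by a stated rule. The synopsis already treats discontinued subjects as not improved, which points to failure.

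If the sponsor prefers closure by Visit 4 without durability, 13.2 should say that instead. Either way, one rule should be fixed before the interim analysis.

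In the synopsis, put this definition under the primary endpoint and replace closure under the secondary endpoints with time to closure, as in sections 4.2 and 5.1. Footnote 5 of the Schedule of Assessments must be reconciled with sections 5.1 and 14.4 on who is crossed over at Visit 4.

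The cost is wording only: no added visits, procedures or subjects. The downside is a possibly lower closure rate. The plan states no design closure rates, so it cannot be told whether its power statements refer to closure by Visit 4 or to durable closure; the sponsor should confirm which.

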- 3) Place a human fibroblast growth factor-2 (FGF-2) soaked pledget of bioabsorbable gelatin sponge larger than the tympanic membrane so the tympanic membrane is completely covered.
- 4) Secure the pledget in place with several drops of fibrin glue.
- 5) After the effects of the topical anesthetic have worn off, if any, the patient is released with the following instructions:
 - a) Avoid violently sniffling or blowing the nose
 - b) Sneeze and cough naturally through the mouth without occluding the mouth with the hand.
 - c) Use cotton balls covered with petroleum jelly on the outer surface when washing the hair and bathing. This is needed to help keep water out of the ear.
 - d) Avoid using a hearing aid in the treated ear.
 - e) Avoid flying, using elevators in tall buildings, and other situations involving substantial changes in air pressure.
 - f) Avoid swimming.

DISCONTINUATION FROM TREATMENT:

Reasons for permanent discontinuation include the following:

If the first treatment does not result in complete closure, subsequent treatments will not be administered if any ear complications occur in the treated ear, including but not limited to infection, moderate to severe pain, moderate to severe irritation, or clinically significant sensorineural hearing loss. All subjects will complete all safety follow up visits.

PRIMARY ENDPOINT:

The tympanic membrane and surrounding structures will be examined every 21-days (+7 days) for up to three visits. Adverse events will be recorded at all visits. Routine laboratory tests will be performed at the screening visit and at the final study visit. Vital signs will be assessed at each study visit and changes in clinical examination findings will be noted.

SECONDARY ENDPOINTS:

- Tympanic membrane perforation closure determined by otoscopic exam and photographic documentation
- Pure-tone and speech discrimination scores as measured by pre- and post-treatment audiograms
- Mobility of the tympanic membrane as measured by tympanometry
- Salvage rate of FGF-2 in patients who fail placebo

STATISTICAL ANALYSIS:

The target enrollment of 75 subjects will provide sufficient power while also accounting for potential retention issues. The primary endpoint is to confirm the efficacy of

FGF-2 in subject with TMR by testing the hypothesis that the rate of subject with complete closure of the TMR will be superior to that placebo.

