Up to 50 percent of TMPs are refractory to spontaneous healing and require surgical repair depending upon the etiology of the perforation. There is a higher incidence of middle ear contamination with resultant increased incidence of acute and chronic otitis media and chronic middle ear scarring or tympanosclerosis with a resultant conductive hearing loss. Profound sensorineural hearing loss, balance dysfunction, meningitis or brain abscess are rare but serious complications, which may occur from middle ear infection. Long-term effects may include speech and language acquisition delay in children as well.

Some subjects undergo multiple attempts at surgical repair without attaining closure of the tympanic membrane. The underlying cause of the perforation may be an important factor in the inability of the body to spontaneously close the perforation or the surgeon's inability to get engraftment and surgical closure. For example, traumatic perforations of the tympanic membrane generally, close spontaneously within three months of the injury. Perforations caused by hot slag burns in welders are notoriously difficult to get to heal even with surgical intervention. Blast injuries from improvised explosive devices spontaneously heal in less than 50% of cases. The latter two conditions may be due to poor vascularity of the cauterized remnant TM and damaged external auditory canal skin.

Other etiologies such as acute otitis media, poor eustachian tube function, or retained tympanostomy tubes can predispose to chronic perforations as well. Ingrowth of squamous epithelium from the outer layer of the TM around the edge into the middle ear through the perforation preventing fibroblast proliferation and contraction of this wound may prevent spontaneous healing also. While small perforations are not usually associated with hearing loss, large perforations can be associated with a significant conductive hearing loss (up to 30 dB SPL).

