3.2 Clinical Use of FGF-2

A study in 87 subjects with chronic tympanic membrane perforation was recently published. The objectives of the study was to measure the rate of complete closure of chronic TMR using basic fibroblast growth factor (bFGF) combined with an atelocollagen/silicone bilayer membrane patch. The study assessed closure of TMR in 87 subjects using bFGF, which is thought to promote the regeneration of TM tissues by facilitating the growth of fibroblasts and collagen fibers. A dose of 10 mcg of bFGF was administered every 21-days. Study methods included a procedure using an operating microscope. The results of the study reported mean perforation size before treatment of 14.4%. Complete closure of the TMR was achieved in 80 subjects (92.0%), whereas pinholes remained in 5 subjects (5.7%), and small perforations were observed in 2 subjects (2.3%). In the subjects with complete closure, the TMR closed after an average 1.8 treatments, and hearing improved by 13.6 dB. In conclusion the study demonstrated that bFGF combined with atelocollagen is effective for the conservative treatment of TMR (Hakuba et al, 2009).

Kanemaru et al (2011) have reported updated findings from their 2009 presentation involving 63 subjects, in which 53 received tympanic membrane repair using gelatin sponge and fibrin glue with b-FGF and 10 were assigned to the control group of gelatin sponge and fibrin glue alone. The study sought to determine closure rates, hearing level, and sequelae after 3 weeks post treatment. Of the 53 subjects who received b-FGF treatment, 52 had a complete closure of the TMP (98.1%) compared to 1 out of 10 (10%) of the control group subjects. Hearing level improved for all subjects with successful TM repair. No serious sequelae were observed. Some of the perforations were pan tympanic and included loss of nearly all of the tympanic membrane. They concluded that bFGF may be a simple, cost-effective treatment option for subjects with chronic tympanic membrane perforations. Human FGF-2 has been the most studied FGF isoform and its production and clinical applications in wound healing are well described.

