5.1 Overall Study Design and Plan Description

This study is a double blinded, placebo controlled phase II study evaluating the efficacy of FGF-2 for the treatment of chronic non-healing tympanic membrane perforations (TMP). The documentation of TM closure will be the main efficacy outcome measure. Pretreatment photographs will document the area of the TM perforation and allow measurement of surface areas of the TMP for comparison of pre- and post-treatment. The study will be divided into two phases, the Randomized Treatment phase (part A), and the Unblinded Crossover phase (part B). In part A of the study, subjects will be randomized 3:1 to receive FGF-2 or placebo treatment up to 3 treatments. Subjects that fail three study treatments will move on to part B of the study. Subjects who received placebo in part A and failed three placebo treatments will crossover to receive unblinded FGF-2 for up to 3 treatments. Subjects who received FGF-2 in part A and failed three experimental treatments will not have additional FGF-2 treatment, and will move on to study follow up.

The primary outcome for the study will be to determine the TMP closure efficacy of FGF-2 and placebo, with up to 3 treatments each. The OBD was determined to be 100 μ g of FGF-2 per 1 mL with an estimated dose of about 20 μ g in 0.2ml in prior studies by [name] (Kanemaru et al., 2011).

Secondary outcomes for the study include: (1) Determination of the time to closure of tympanic membrane perforation, (2) Measurement of changes in pure-tone and speech discrimination scores, (3) Determination mobility of tympanic membrane as measured by tympanometry, and (4) Observation of salvage rate of FGF-2 treatment in subjects who failed placebo treatment.

If both ears are affected by chronic perforation, only one ear will be initially enrolled in the study and receive treatment. The ear with the more significant symptoms will be the one enrolled in the study (i.e., greater conductive hearing loss). The non-study ear will not be enrolled or undergo additional treatments during the study period.

- 1) In an outpatient examination, the subject will be confirmed to have a tympanic membrane perforation by microscopic otoscopy and that no active infection and/or inflammation is present. Then a cotton ball soaked in 4% lidocaine jelly will be inserted with micro alligator forceps directly to the surface of the tympanic membrane under microscopic visualization.

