7.3 Removal of Subjects from Treatment or Assessment

Reasons for permanent discontinuation include the following:

If three treatments do not result in complete closure, subsequent treatments will not be administered if any ear complications occur in the treated ear, including but not limited to, infection, requires other surgery, moderate to severe pain, moderate to severe irritation, clinically significant hearing loss. All subjects will complete all safety follow-up visits.

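### The criterion for a clinically significant hearing change has no direction, so the expected benefit of closure meets it as readily as harm; hearing worsening is not planned as a safety table, and the two discontinuation texts disagree on type of loss

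*Combined protocol and SAP*

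**What the plan says.** - **Criterion.** Section 13.2 gives the only numerical rule in the documents for a clinically significant hearing change: "A change of >10 dB across two frequencies or a change in speech discrimination of" more than 20%. The word is change for both limbs; neither says better or worse.
- **Measurement.** The same section states: "Audiometric studies including pure tones (0.25, 0.5, 1, 2, 4, and 8 kHz) and speech discrimination scores will be recorded pretreatment and post treatment". It does not say whether the tones are air or bone conduction. Bone conduction and the air-bone gap are not mentioned anywhere in the documents.
- **Expected benefit.** Section 3.2 reports, for the cited 87-subject study, that in subjects with complete closure "the TMR closed after an average 1.8 treatments, and hearing improved by 13.6 dB". The Introduction (Section 2) puts the conductive loss from large perforations at up to 30 dB.
- **Safety.** Section 13.3 lists adverse events, laboratory tests and vital signs. Section 18 assesses safety from adverse events and laboratory results. Neither names audiometry.
- **Use of the type of loss.** The synopsis, under discontinuation, refers to "clinically significant sensorineural hearing loss". Section 7.3 refers to "moderate to severe irritation, clinically significant hearing loss". Section 5.1 chooses the study ear in bilateral disease by symptoms, with "greater conductive hearing loss" as the example.
- **Trigger of the discontinuation text.** The synopsis starts from failure of the first treatment to close the ear; Section 7.3 starts from failure of three treatments.

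**The concern.** Closing a perforation is expected to improve hearing, while a drug placed next to the middle ear may conceivably harm it. A hearing criterion in this trial has to tell those two apart. One that counts any shift does not: an ear that gains and an ear that loses the same number of decibels receive the same label.

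Two omissions add to this. Hearing worsening has no planned place in the safety output. And because the conduction type is not specified, the plan does not secure the information needed to separate a sensorineural from a conductive loss, although the synopsis and Section 5.1 both rely on that distinction.

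The difference between the synopsis and Section 7.3 is a separate matter. A conductive loss judged clinically significant meets the wording of Section 7.3 but not that of the synopsis. Under the Schedule of Assessments (13.1, footnote 1) the audiogram precedes dosing at each treatment visit, so the discrepancy can affect who is treated again.

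**Working it through.** No sample size, power or significance level in the plan depends on this criterion, so there is no stated figure to reproduce. The check applies the Section 13.2 rule to the protocol's own numbers.

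**Inputs.** Threshold: more than 10 dB (Section 13.2). Mean gain on closure: 13.6 dB (Section 3.2). Largest conductive loss available for recovery: 30 dB (Section 2).

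**Step 1: does expected benefit meet the criterion?** 13.6 − 10 = 3.6 dB above the threshold. A uniform gain of 13.6 dB meets the rule at every tested frequency, as improvement.

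**Step 2: what would air conduction alone show in a closed ear?** Let G be the conductive gain and L the inner-ear loss, both taken as uniform over frequencies. The net change is G − L.

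- It reads as a significant gain when G − L > 10, that is L < G − 10.
- It reads as a significant loss when L − G > 10, that is L > G + 10.
- Between these limits the pure-tone limb gives no flag.

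| G (dB) | Reads as gain if L is below | No pure-tone flag | Reads as loss if L is above |
|---|---|---|---|
| 13.6 | 13.6 − 10 = 3.6 | 3.6 to 23.6 | 13.6 + 10 = 23.6 |
| 30 | 30 − 10 = 20 | 20 to 40 | 30 + 10 = 40 |

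**Step 3: illustration when gains vary.** The documents give no standard deviation. Assume normal changes at the six frequencies with SD 5 to 12 dB and inter-frequency correlation 0.3 or 0.7, and flag a subject when at least two frequencies move more than 10 dB in the same direction.

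- A mean gain of 13.6 dB is flagged in about 80% to 96% of subjects, nearly all for improvement.
- An assumed 15 dB inner-ear loss with no conductive gain is flagged as worsening in about 81% to 99%.
- The same loss with the 13.6 dB gain present is flagged as worsening in about 5% to 40%, and as a gain in about 1% to 28%.

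These percentages depend on the assumed values. Steps 1 and 2 use only the protocol's figures and the uniformity assumption.

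**Step 4: the two discontinuation texts side by side.**

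| | Synopsis | Section 7.3 |
|---|---|---|
| Type of loss | sensorineural | any |
| Starts after | first treatment | three treatments |
| Threshold given | none | none |
| Refers to Section 13.2 | no | no |

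**The case against.** The case on the other side is substantial, and it rules out several stronger readings that a reader might infer.

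- **That the trial will report a pooled rate of significant changes, higher in the arm with more closures.** No section plans such a rate. The secondary endpoint is the scores and their changes, which carry a sign. Section 17.6 names a test for categorical data but no hearing category. The defect lies in the criterion and in anything built on it, not in a planned analysis.
- **That a hearing gain could stop treatment.** It could not. Both discontinuation texts say loss, and neither refers to Section 13.2. The adverse-event definition in Section 15.1 also covers unfavorable changes.
- **That masking defeats the discontinuation rule.** The 13.6 dB gain belongs to ears with complete closure. The discontinuation text concerns ears that have not closed, and closed ears receive no further treatment. Masking therefore bears on safety reporting in closed ears.
- **That bone conduction will not be measured.** The documents are silent, which is not the same as excluding it. Section 13.2 introduces the pure tones as included among the audiometric studies, and the use of conductive and sensorineural loss elsewhere implies that someone will separate them. But nothing requires it or says it will be reported. Section 24.1 treats audiograms as routine care and Section 26 names two sites, so the protocol does not secure uniform content.
- **That a baseline speech score of 80% or more rules out a speech improvement.** This holds only if 20% means percentage points (100 − 80 = 20, which is not more than 20). Read as a relative change, a score above 80 × 1.2 = 96 would qualify. The text does not say which is meant.

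The 13.6 dB figure also has limits. It comes from a different carrier and a 10 mcg dose, with no frequencies or spread stated. The Introduction says that "small perforations are not usually associated with hearing loss", and entry sets no minimum hearing loss or perforation size, so some ears will have little gain either to count or to mask. The speech limb may catch some inner-ear losses that the tones miss.

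What remains is the missing direction, the unspecified conduction type, the absence of audiometry from the safety measurements, and the disagreement between the synopsis and Section 7.3.

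**Conclusion.** The point holds in this form. As written, the Section 13.2 criterion cannot distinguish benefit from harm, and the protocol's own mean gain on closure exceeds its threshold by 3.6 dB. If only air conduction is recorded and the gain is a uniform 13.6 dB, inner-ear losses of 3.6 to 23.6 dB in closed ears pass the pure-tone limb unflagged. That range is conditional on both assumptions and on the cited study's gain carrying over to this product.

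The synopsis and Section 7.3 contradict each other on the type of hearing loss and on the number of treatments after which the text applies. This review does not say which is right.

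The weight is minor to moderate. A secondary endpoint and a safety read-out are affected; the sample size and the primary closure analysis are not.

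**What to change.** 1. In Section 13.2, replace the single undirected criterion with two reporting categories, improvement and worsening, each at the protocol's existing thresholds. A subject who meets both is counted in both.
2. Add hearing worsening to Section 13.3 and tabulate it by arm with the safety data.
3. State whether the pure-tone thresholds are air or bone conduction. Where bone conduction is recorded, report it separately.
4. Reconcile the synopsis and Section 7.3 on the hearing-loss wording and on first treatment versus three treatments. Say whether Section 13.2 defines clinically significant in those texts. The choice of rule belongs to the sponsor and the investigators.

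The cost is protocol wording, a little more tabulation and smaller counts in each category. No change to sample size, power or significance level follows.
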